Care Provider: Therapists administering interventions are unblinded.

None (Open Label): Not applicable; partial blinding is used.

6. Allocation

Participants are randomly assigned to BFR-RT or T-RT groups.

Method: Opaque envelopes with coded assignments prepared by an independent team member.

Stratification: Not specified, but typically balanced for age, sex, or baseline function.

7. Enrollment

- Target Sample Size: 32 participants.

Type: Actual (confirmed enrolled participants).

Justification: Based on power analysis to detect clinically significant differences in muscle hypertrophy/strength.

8. Additional Protocol Details

Intervention Protocol

Frequency: Biweekly sessions (16 total over 8 weeks).

BFR Technique:

- Occlusion band placed proximally on the affected limb.
- Tightness standardized to allow one finger beneath the band.

Standard Rehabilitation:

- Includes range of motion (ROM) exercises, strengthening, and functional training per hospital protocol.

Outcome Assessments

Time Points: Baseline (Week 0-1), Mid-Intervention (Week 4-5), Post-Intervention (Week 9).

Measures:

Primary: Muscle hypertrophy (ultrasound/MRI), strength (manual muscle testing).

Secondary: Pain (KOOS), knee ROM, effusion (circumference), adherence rates.

Safety Monitoring

- Adverse Events: Documented throughout; none reported in this trial.
- Exclusion Safeguards: No vascular pathologies or anticoagulant use.

9. Ethical Considerations

Informed Consent: Obtained from all participants.

Approval: Ethical approval was taken from the Institutional Review Board (IRB) of Rehman Medical Institute.

10. Participants:

- **Inclusion criteria:** Individuals who have undergone ACL reconstruction surgery within the past 4 weeks, free of any neurological impairments or significant cardiac, pulmonary, or metabolic conditions.
- **Exclusion criteria:** Individuals with contraindications to exercise, any other comorbidity, or systemic inflammatory conditions.

Outcome Measures:

- **Primary Outcome:** Muscle strength (measured using manual muscle technique). Muscle size (measured via measuring tape), ROM (Using goniometer), pain (using a Visual Analog Scale), and joint effusion (assessed clinically).

Statistical Analysis Plan

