This Statistical analysis plan (SAP) compares postoperative rehabilitation outcomes between an experimental training group (n=16) and a control group (n=16) across three key timepoints: immediate post-surgical baseline (0-1 week), mid-intervention (4-5 weeks), and post-intervention (8-9 weeks). The study employs a repeated measures design to evaluate five primary outcome domains: muscle size (continuous, cm), range of motion (continuous, degrees), muscle strength (ordinal, 0-5 scale), pain perception (ordinal, VAS 0-10), and joint effusion (ordinal, 0-3 clinical scale).

In contrast, This SAP includes descriptive statistics, normality assessments, inferential statistical tests with corresponding assumptions, multiple comparison adjustments, missing data handling procedures, and software implementation to ensure reproducibility.

1. Descriptive Statistical Approaches

Comprehensive descriptive analyses will precede all inferential testing to characterize the dataset and inform appropriate test selection. For continuous variables (muscle size, ROM), we will report means with standard deviations (SD) for normally distributed data and medians with interquartile ranges (IQR) and full ranges for non-normal distributions, supplemented by graphical representations including boxplots with superimposed individual data points to visualize both group trends and individual trajectories. Ordinal variables (strength, pain, effusion) will be summarized using median scores with IQRs and frequency distribution tables showing counts/proportions at each ordinal level, with stacked bar charts employed to visualize proportional changes across timepoints. These descriptive analyses will be stratified by group (experimental vs control) and timepoint to enable preliminary assessment of intervention effects and data distributions prior to formal hypothesis testing.

2. Data Characteristics and Variable Classification

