4.1 Within-Group Longitudinal Analyses

For evaluating changes over time within each experimental arm, distinct approaches will

be employed based on variable characteristics. Continuous variables meeting normality assumptions will be analyzed using repeated measures ANOVA with Greenhouse-Geisser correction for sphericity violations, followed by paired t-tests with Bonferroni-adjusted α levels for post-hoc timepoint comparisons when omnibus tests reach significance. Non-normal continuous data and all ordinal outcomes will utilize the Friedman test (non-parametric equivalent to repeated measures ANOVA) followed by Wilcoxon signed-rank tests for post-hoc comparisons with appropriate multiplicity adjustments. Effect sizes will be reported as Cohen's d for parametric analyses and rank-biserial correlations for non-parametric tests to quantify the magnitude of observed changes independent of sample size considerations.

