4.2 Between-Group Comparative Analyses

Experimental versus control group comparisons at each timepoint will employ independent samples t-tests for normally distributed continuous variables with equal variances, Welch's t-tests for unequal variances (as determined by Levene's test), and Mann-Whitney U tests for non-normal continuous or ordinal data. Between-group effect sizes will be reported as mean differences with 95% confidence intervals for parametric tests and Hodges-Lehmann median differences for non-parametric analyses. To account for baseline imbalances in this pilot study, exploratory analyses of covariance (ANCOVA) may be conducted for continuous outcomes using baseline measurements as covariates if substantial pre-intervention group differences are detected despite randomization.

5. Missing Data Handling Protocol

Missing data patterns will be formally evaluated using Little's MCAR test prior to primary analyses. Given the pilot nature of this study with limited sample size, primary analyses will employ complete case approaches with explicit reporting of missing data proportions by group and timepoint. Sensitivity analyses will compare complete case results with multiple imputation approaches using chained equations (MICE)

incorporating baseline characteristics and observed follow-up data as predictors. Participants with missing baseline data will be excluded from all analyses, while those missing later timepoints will be retained for analyses where their available data permits. A participant flow diagram will document attrition at each study phase.

6. Software Implementation and Reproducibility

All analyses will be conducted using Stata MP 18.0. Graphical outputs will adhere to STROND guidelines for transparent reporting of non-normal data distributions.

Reference:

Ardern, C. L., Webster, K. E., Taylor, N. F., & Feller, J. A. (2011). Return to sport following anterior cruciate ligament reconstruction surgery: A systematic review and meta-analysis of the state of play. *British Journal of Sports Medicine*, 45(7), 596–606. <https://doi.org/10.1136/bjsm.2010.076364>

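### Does the missing definition of week zero, set against a four-week entry window after surgery, leave the analysis visits without a usable time origin?

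*Combined protocol and SAP*

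**What the plan says.** The opening paragraph of the SAP gives the timepoints as "immediate post-surgical baseline (0-1 week), mid-intervention (4-5 weeks), and post-intervention (8-9 weeks". The protocol's Outcome Assessments (section 8) has "Time Points: Baseline (Week 0-1), Mid-Intervention (Week 4-5), Post-Intervention (Week 9", with no origin stated. The inclusion criterion in section 10 is "Individuals who have undergone ACL reconstruction surgery within the past 4 weeks". The Intervention Protocol in section 8 gives "Frequency: Biweekly sessions (16 total over 8 weeks", which is two sessions a week.

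Four other statements bear on the point:

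- Section 6 (Allocation) says "Stratification: Not specified, but typically balanced for age, sex, or baseline function"; time since surgery is not among the examples.
- SAP section 4.1 introduces its repeated-measures tests with "For evaluating changes over time within each experimental arm".
- SAP section 4.2 compares the arms at each timepoint and adds that "exploratory analyses of covariance (ANCOVA) may be conducted for continuous outcomes using baseline measurements as covariates", on condition that the groups differ substantially at the start.
- SAP section 5 states "Participants with missing baseline data will be excluded from all analyses".

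**The concern.** The SAP's description of baseline points to surgery as the start of the clock, while its names for the other two visits point to the start of training. The entry criterion fits the first reading only if every patient came in during the first week, which no section says.

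If weeks ran from surgery, a patient entering at week 4 would have no baseline in the 0-1 week window and would be only part-way through training at the final visit. Section 5 does not say whether a baseline outside its window counts as missing, and with 16 patients per arm each exclusion would matter. If weeks ran from entry, patients at different stages of recovery would share a visit label, and neither the allocation nor the optional ANCOVA takes time since surgery into account. The final visit is also written in two ways. The risk would be that two analysts build different datasets, or that a chance difference in recovery time distorts the arm comparison.

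**Working it through.** **Inputs.** Visit windows 0-1, 4-5 and 8-9 weeks (SAP introduction); entry up to 4 weeks after surgery (protocol section 10); 16 sessions over 8 weeks, or 16/8 = 2 per week (section 8); 16 patients per arm (SAP introduction). Entry times are not given.

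**1. Do the plan's windows fit together?** Baseline 0-1 plus 4 weeks gives 4-5; plus 8 weeks gives 8-9. Both SAP windows are reproduced exactly. They are coherent if the clock starts at about the first session.

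**2. Surgical clock.** A week-4 entrant has had 8 - 4 = 4 to 9 - 4 = 5 training weeks, or 8 to 10 of 16 sessions, at a visit named post-intervention. The same patient would be starting training at the visit named mid-intervention. The visit names make no sense for such a patient, so this reading is the poorer one.

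**3. Entry clock.** Adding 0-4 weeks of entry delay to each window gives time since surgery of 0-5, 4-9 and 8-13 weeks. Adjacent ranges overlap by one week, but only between different patients. Within a patient, successive visits are between 4 - 1 = 3 and 5 - 0 = 5 weeks apart. Repeated-measures ANOVA, Friedman and Wilcoxon signed-rank tests compare each patient with himself or herself, so the overlap does not invalidate them.

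**4. Chance imbalance between arms.** Assume entry uniform over W days. The SD is W/√12, and the 95% limit for the difference in arm means is 1.96 × SD × √(2/16).

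| W (days), assumed | SD (days) | 95% limit (days) |
|---|---|---|
| 7 | 2.02 | 1.4 |
| 14 | 4.04 | 2.8 |
| 28 | 8.08 | 5.6 |

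Assume also that 8.08 days of recovery moves an outcome by 0.1 to 0.5 SD. An imbalance at the limit then shifts the comparison by 1.4/8.08 × (0.1 to 0.5) = 0.02 to 0.09 SD for W = 7, and by 5.6/8.08 × (0.1 to 0.5) = 0.07 to 0.35 SD for W = 28.

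**5. Is that shift additional error?** The ordinary 95% chance margin with 16 per arm is 1.96 × √(2/16) = 0.69 SD. In the worst case above, time since surgery supplies 0.35 of it and everything else supplies √(0.69² - 0.35²) = 0.60. The two combine in quadrature to 0.69; they do not add to 1.04. The t-test's standard error already contains the imbalance.

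**6. Would a days-from-surgery covariate help?** Simulated ANCOVA with N = 32 and entry over 0-28 days gave these standard errors for the arm difference, without and with the covariate:

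| Residual correlation, assumed | Without | With | Change |
|---|---|---|---|
| 0 | 0.362 | 0.368 | +1.7% |
| 0.3 | 0.358 | 0.348 | -2.8% |
| 0.5 | 0.364 | 0.319 | -12.4% |

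The gain depends wholly on a correlation that the documents do not give, and at zero it is a small loss.

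**The case for a change.** The strongest case for acting is that the textual facts are not in dispute. The baseline label and the entry window agree only if everyone entered in the first week, no section defines week zero, and the final visit is Week 9 in one place and 8-9 weeks in another. Clarification would cost little, since the surgery date is needed to check eligibility, and a table of days from surgery by arm would help a reader.

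That stands as a remark on wording. The consequences drawn from it do not:

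- **Different datasets.** The plan has one assessment per named visit, and the tests treat visit as a category. There is nothing to reassign. Missing baseline data in section 5 naturally means that no measurement was taken; treating a late one as missing would need a window rule that the SAP does not contain.
- **Mixed recovery stages within an arm.** This adds heterogeneity. Within-arm change includes natural recovery whichever clock is used, so a stated origin would not remove it.
- **Covariate adjustment.** It would enter an ANCOVA that is exploratory, conditional and limited to the two continuous outcomes. The t-tests, the rank tests and the within-arm analyses would be as they are now. Since section 7 of the protocol lists enrolment as actual, a covariate added now could also look post hoc.
- **Final visit.** The ninth week is the interval from 8 to 9 elapsed weeks. The notation is loose, but both entries denote the same post-intervention assessment.

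**Conclusion.** No change to the plan follows. The undefined week zero is a gap that an analyst would fill sensibly from the visit names and the 8-week course, and the description of baseline as immediately after surgery is a loose label that may be inaccurate for late entrants. The entry limit is an upper bound, so the two statements need not conflict for any patient actually enrolled; the documents do not give entry times that would settle this.

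On the entry clock the effect is a possible spread of up to 5 weeks in time since surgery at each visit. Randomisation balances it in expectation, and chance imbalance lies inside the ordinary 0.69 SD margin for 16 per arm. The 0.35 SD figure needs three assumptions at once: uniform entry over 28 days, 0.5 SD of recovery per 8.08 days, and an imbalance at its 95% limit.

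The conclusion rests on reading weeks from entry or first session and on one assessment per patient per visit. Stating the origin, aligning the label and the final-visit notation, and tabulating days from surgery by arm would make the report easier to read, but would alter no planned test or estimate.

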Low-load blood flow restriction (LL-BFR) training has emerged as an innovative rehabilitation strategy that combines low-intensity resistance exercise with partial vascular occlusion to enhance muscle growth and strength while using much lower loads than traditional resistance training (Hughes et al., 2017). Evidence suggests that BFR can safely stimulate muscle hypertrophy comparable to high-load training and may reduce joint stress, making it particularly suitable for patients recovering from ACLR (Scott et al., 2015). This pilot study aims to compare the effectiveness of LL-BFR and traditional resistance training in improving muscle size, strength, range of motion, pain, and joint effusion in patients following ACLR, contributing to the evidence base for optimal post-surgical rehabilitation strategies.

Objective

The main objective/s of the study is to compare the effectiveness of low load blood flow restriction training (LL-BFR) with traditional resistance training exercises (T-RT) at improving skeletal muscle hypertrophy, strength, Range of motion (ROM), pain and effusion in individuals who have undergone anterior cruciate ligament (ACL) reconstruction surgery.

Study Design

1. Study Type

Interventional: The study (Pilot randomized controlled trial) involves an active intervention (BFR-RT vs. T-RT) to evaluate treatment efficacy.

2. Primary Purpose

Treatment: The study aims to assess the therapeutic effectiveness of BFR-RT compared to traditional low load training in improving post-ACLR outcomes.

3. Study Phase

N/A: The trial does not involve investigational drugs or biologics.

4. Intervention Model

Parallel Design: Two distinct groups receive different interventions simultaneously:

Group 1 (BFR-RT): Low-load resistance training with blood flow restriction along with standard rehabilitation.

Group 2 (T-RT): Low-load traditional resistance training with standard rehabilitation.

- **Model Description:**

BFR-RT group undergoes 8 weeks of BFR training followed by standard rehabilitation protocol progression.

T-RT group receives standard rehabilitation alone for the entire duration.

5. Number of Arms

2 Arms:

Experimental Arm: BFR-RT.

Active Comparator Arm: T-RT.

6. Masking (Blinding)

- **Single-Assessor Blinded:**

Investigator: The researcher assessing outcomes is blinded to group assignments.

Participant: Participants are aware of their group (open-label for participants).

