The dataset comprises both continuous and ordinal variables requiring distinct analytical approaches. Continuous variables including muscle circumference (measured via standardized tape measure protocol) and active range of motion (measured via goniometry by blinded assessors) will be analyzed for both central tendency and variability. Ordinal variables including manual muscle testing scores (Medical Research Council 0-5 scale), visual analog pain scores (recorded as integers 0-10), and clinician-rated effusion scales (0=none, 3=severe) will be analyzed using non-parametric methods due to their inherent rank-based properties and expected non-normal distributions. All variables will be assessed at three protocol-specified timepoints with identical measurement protocols maintained across groups to ensure comparability.

3. Normality and Parametric Assumption Testing

Formal statistical testing for normality assumptions will be conducted for all continuous variables prior to selecting inferential methods. The Shapiro-Wilk test ($\alpha=0.05$) will be applied to residuals from all continuous outcome measures within each group-by-time combination, supplemented by visual inspection of Q-Q plots and histograms to detect deviations from normality that may not reach statistical significance in small samples. Homogeneity of variance between groups will be verified using Levene's test for equality of variances when parametric between-group comparisons are planned. For instances where normality or homogeneity assumptions are violated (Shapiro-Wilk $p\leq0.05$ or Levene's $p\leq0.05$), pre-specified non-parametric alternatives will be implemented as detailed in subsequent sections. All assumption testing results will be documented in supplementary materials to demonstrate the appropriateness of selected analytical methods.

4. Primary Inferential Statistical Methods

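### For muscle size and ROM, the SAP lets the between-group test be chosen after an arm-labelled look at the effect; the inflation is small unless ANCOVA also competes

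*Combined protocol and SAP*

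**What the plan says.** SAP section 1 opens with the order of work: "Comprehensive descriptive analyses will precede all inferential testing to characterize the dataset and inform appropriate test selection". It closes by saying that the same tables are "stratified by group (experimental vs control) and timepoint to enable preliminary assessment of intervention effects and data distributions prior to formal hypothesis testing". So one set of tables, split by named arm, serves both test selection and a first view of the effect.

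SAP section 3 gives a numeric rule for the continuous outcomes. Shapiro-Wilk at 0.05 "will be applied to residuals from all continuous outcome measures within each group-by-time combination". If it or Levene's test gives p<=0.05, "pre-specified non-parametric alternatives will be implemented as detailed in subsequent sections". The numeric check is "supplemented by visual inspection of Q-Q plots and histograms to detect deviations from normality that may not reach statistical significance in small samples".

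SAP section 4.2 offers the t-test, Welch's test and Mann-Whitney for continuous data. It sends unequal variances to Welch, whereas section 3 sends them to a non-parametric test. It also allows an exploratory ANCOVA when baseline imbalance is large enough, without saying how large.

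On masking, the protocol (6. Masking) says: "The researcher assessing outcomes is blinded to group assignments". Participants know their group, and "Therapists administering interventions are unblinded". Neither the protocol nor the SAP mentions the person who analyses the data.

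**The concern.** A test counts as pre-specified only if the choice among candidates cannot depend on the observed difference between arms. Here the labelled tables come first, are said to inform the choice, and are also meant to show the effect. Visual inspection is aimed at exactly the cases where the numeric trigger has not fired, and nothing says which prevails. An analyst who has seen the difference could call a plot non-normal, or not, according to which test looks better, and still be following the SAP.

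Muscle size and ROM are two of the five primary domains listed in the SAP's introduction. At stake is whether their between-group p-values can be read at face value.

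**Working it through.** **1. Where a choice exists.**
- Strength, pain and effusion: SAP sections 2, 4.1 and 4.2 fix non-parametric tests, so there is no choice.
- Muscle size and ROM: the choice is open through visual inspection without a criterion, the Levene conflict between sections 3 and 4.2, and the optional ANCOVA.
- Two outcomes at two follow-up visits give 2 x 2 = 4 affected treatment comparisons.

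**2. Can the numeric trigger follow the effect?** No. Shapiro-Wilk is run on residuals within each arm and visit, and Levene's test compares spreads. Neither changes if a constant is added to one arm. Any dependence on the effect must come through the discretionary steps.

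**3. Size under the null.** The SAP states no significance level for the between-group tests, so two-sided 5% is assumed, in line with its 95% confidence intervals. The arm sizes, 16 and 16, are from the SAP introduction. Distributions and the baseline to follow-up correlation (rho) are assumptions. Each scenario has 20,000 simulated trials with no treatment effect, one outcome and one follow-up visit:

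y = rho x b + sqrt(1 - rho^2) x e, with b and e either standard normal or standardised gamma with shape 2.

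The gamma has skewness 2/sqrt(2) = 1.41, so at rho = 0.6 y has skewness 1.41 x (0.6^3 + 0.8^3) = 1.41 x 0.728 = about 1.0.

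Strategies compared:
- A: numeric rule applied mechanically, Levene p<=0.05 to Mann-Whitney (SAP section 3).
- B: the same, but Levene p<=0.05 to Welch (SAP section 4.2).
- C: B with selective visual override. If Shapiro-Wilk fires, Mann-Whitney is used; otherwise the smaller p of Mann-Whitney and t (or Welch).
- D: smaller p of t and Mann-Whitney, trigger ignored.
- E: smaller p of C and ANCOVA.

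| Scenario | Shapiro-Wilk fires in either arm | A | B | C | D | E |
|---|---|---|---|---|---|---|
| Normal, rho 0.6 | 9.6% | 5.01% | 5.04% | 5.66% | 5.72% | 8.19% |
| Skewed, rho 0.6 | 41.9% | 5.08% | 5.34% | 5.58% | 5.96% | 8.13% |
| Normal, rho 0.8 | 9.8% | 4.92% | 4.96% | 5.68% | 5.80% | 9.19% |

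The normal-data trigger rate agrees with 1 - 0.95^2 = 9.75%. Each test used alone gave 4.6 to 4.9%.

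**4. What discretion adds.** Like for like, C minus B is 5.66 - 5.04 = 0.62, 5.58 - 5.34 = 0.24 and 5.68 - 4.96 = 0.72 percentage points. Further runs under similar assumptions gave 5.3 to 5.9% for selective override and 5.7 to 6.1% with the trigger ignored, hence about 5.3 to 6% overall. Adding ANCOVA gave 8.1 to 9.2% across all runs (correlations 0.5 to 0.8).

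**5. The Levene conflict.** Levene's test fired without Shapiro-Wilk, so that the two sections prescribe different tests, in 3.3 to 3.5% of null comparisons.

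**The case against.** The strongest reply is that section 1 never tells anyone to choose by the effect. Its closing sentence names distributions as well as effects, and the natural link to test choice is the distributions. Section 3 supports this by tying the choice to numeric triggers that cannot respond to the arm difference. Applied mechanically, those rules hold the error at 4.9 to 5.3%. The SAP also promises to publish the assumption checks. ANCOVA is labelled exploratory and depends on baseline imbalance, not on the outcome.

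Much of this stands. A reader might infer that the plan directs an effect-driven choice; the text only permits one. A reader might extend the point to all five primary domains; three have fixed tests. A reader might take the analyst to be known to be unmasked; the documents are silent. And a reader might quote 8 to 9% as the plan's error rate; that requires promoting ANCOVA against its stated role, and it cannot arise at baseline, where the covariate would be the outcome itself.

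What the reply does not remove is the sequence together with the open override. Reporting the assumption checks records the choice afterwards; it does not separate the choice from sight of the effect.

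**Conclusion.** The point holds for muscle size and ROM only. The SAP places a labelled view of effects before test selection, leaves visual judgement without a criterion, and describes no analyst masking, so the test may be chosen with the result in view.

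The consequence is modest: about 5.3 to 6% per comparison in place of 5%. That is a worst case, in which the more favourable result is always kept. A bias towards a positive finding follows only under that assumption; the documents do not show that it would happen. The figure of about 8 to 9% at the follow-up visits applies only if ANCOVA is treated as a competing confirmatory result. All figures rest on 16 per arm, an assumed two-sided 5% level, normal or moderately skewed data, and assumed correlations. The same choice arises in the within-group analyses of section 4.1, which were not simulated.

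It should be corrected because correction costs almost nothing, not because the error is large.

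**What to change.** - **SAP section 1:** remove the early look at intervention effects as a purpose of the tables that come before testing.
- **SAP section 3:** run distribution checks on residuals centred within coded arms, with no between-arm contrast shown. Report visual inspection, but do not let it override the fixed choice.
- **SAP section 4.2:** name one between-group test for muscle size and one for ROM, and sign this off before arm-labelled tables are produced.
- **Levene rule:** make sections 3 and 4.2 agree on what follows p<=0.05. If the fixed test needs no variance pretest, drop the branch.
- **ANCOVA:** state that it is either the fixed primary analysis or supportive only, and remove the undefined imbalance trigger.

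The cost is a short SAP rewording and one coded copy of the dataset, with no extra data. One limit applies. Protocol section 7 gives enrolment as actual, and section 8 already reports that no adverse events occurred, so data may have been in hand when the text was written. If labelled data have been seen, rewording cannot undo that, and the SAP and report should disclose it.

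### Minor, wrong as written: for normally distributed muscle size or ROM with unequal variances, SAP Section 3 requires a non-parametric test and Section 4.2 requires Welch's t-test

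*Combined protocol and SAP*

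**What the plan says.** **SAP Section 3 (Normality and Parametric Assumption Testing).** Levene's test is used to check "equality of variances when parametric between-group comparisons are planned". The consequence follows: "For instances where normality or homogeneity assumptions are violated", defined as Shapiro-Wilk or Levene p<=0.05, "pre-specified non-parametric alternatives will be implemented as detailed in subsequent sections".

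**SAP Section 4.2 (Between-Group Comparative Analyses).** Student's t-test is for normal continuous data with equal variances. The rest of the rule is Welch's "t-tests for unequal variances (as determined by Levene's test), and Mann-Whitney U tests for non-normal continuous or ordinal data". Effects are to be reported as "mean differences with 95% confidence intervals for parametric tests and Hodges-Lehmann median differences for non-parametric analyses".

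**Other routing rules for continuous data.** Section 1 reports "means with standard deviations (SD) for normally distributed data and medians with interquartile ranges (IQR) and full ranges for non-normal distributions". Section 4.1 says: "Non-normal continuous data and all ordinal outcomes will utilize the Friedman test". Neither uses variance homogeneity to choose the route.

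**The concern.** A muscle-size or ROM comparison can satisfy Shapiro-Wilk in both arms and still give Levene p<=0.05. Section 3 then calls for a non-parametric test and Section 4.2 for Welch's t-test. The choice decides the p-value and also what is estimated: a mean difference with a 95% confidence interval, or a Hodges-Lehmann difference with no interval specified. Muscle size and ROM are two of the five primary domains in the SAP's introduction, and that introduction gives reproducibility as an aim. Two analysts following the text could report different results from the same data.

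Section 4.2 also leaves a gap in reporting. It attaches an interval to mean differences only, so the outcomes that always take the rank route have no stated precision for the between-group effect.

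**Working it through.** **1. The rules side by side (between-group, muscle size and ROM)**

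| Shapiro-Wilk | Levene | Section 3 | Section 4.2 |
|---|---|---|---|
| pass | pass | parametric | Student's t |
| pass | p<=0.05 | **non-parametric** | **Welch's t** |
| fail | either | non-parametric | Mann-Whitney |

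Only the second row conflicts. Section 3's pointer to later sections does not settle it, because 4.2 keeps Mann-Whitney for non-normal continuous or ordinal data. Nor can the Levene trigger be meant for another analysis: Section 3 runs Levene only for planned parametric between-group comparisons, and 4.1 does not use it.

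**2. How often, and with what effect**

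The documents give no SDs and no figure to reproduce, so this is an illustration.
- From the SAP: 16 per arm; both assumption tests at 0.05.
- Assumed: normal data; SD ratios of 1 to 2; effects in root-mean-square SDs; Shapiro-Wilk must pass in both arms; Q-Q plots ignored. The SAP does not say how the group-by-time normality results combine.
- Conflict = both arms pass Shapiro-Wilk and Levene p<=0.05. Disagreement = conflict, and Welch and Mann-Whitney fall on different sides of 0.05.

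For SD ratios above 1, the table uses 40,000 comparisons per cell. Ranges cover mean- and median-centred Levene. All figures are percentages of all comparisons.

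| SD ratio | Conflict | Disagree, no effect | Disagree, 0.5 or 1 SD |
|---|---|---|---|
| 1 | 3.4-5.3 | 0.05-0.11 | 0.25-0.44 |
| 1.25 | 8.4-11.3 | 0.15-0.20 | 0.68-1.01 |
| 1.5 | 21.2-26.7 | 0.46-0.61 | 1.62-2.55 |
| 2 | 52.7-59.2 | 1.27-1.46 | 4.36-5.93 |

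The ratio 1 row spans runs of 12,000, 40,000 and 200,000 per cell, because disagreement there is rare. Runs of 3,000 to 6,000 gave somewhat higher values, for example 0.12% with no effect, from 7 events.

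Disagreement is more frequent at an effect of 0.8 SD. At ratio 1, a 3,000-comparison run gave conflict in 6.0% and disagreement in 9.4% of those: 0.060 x 0.094 = 0.0056, or 0.56%. The 200,000-comparison run gave 0.39-0.56%. So disagreement stays below 0.5% at 0, 0.5 and 1 SD in the larger runs and reaches just under 0.6% at 0.8 SD.

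**3. Across the trial**

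There are 2 outcomes x 3 timepoints = 6 such comparisons. If they were independent, which repeated measures are not, the chance of at least one conflict with equal variances would be 1 - (1 - 0.034)^6 = 18.7% to 1 - (1 - 0.053)^6 = 27.9%. This is the chance of having to choose between the sections. The chance that the choice alters significance is far smaller.

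**4. Reach of the missing interval**

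Strength, pain and effusion always go to Mann-Whitney: 3 x 2 = 6 post-baseline comparisons, or 3 x 3 = 9 with baseline, which 4.2 also compares. Any of the 6 muscle-size or ROM comparisons sent to Mann-Whitney is affected too.

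**The case against.** The best defence is that Section 4.2 plainly governs. Section 3 is a general statement that defers to later sections; 4.2 is the specific rule and names Levene's test as the trigger for Welch. Sections 1 and 4.1 also tie the median or rank route to non-normality alone. This stands as the probable intention, and most analysts would follow 4.2. It does not remove the conflict: Welch's test is not a non-parametric alternative, and no sentence gives 4.2 precedence.

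The size of the effect also counts against a strong finding. The conflict needs normality to hold and Levene to reject, in two outcomes, between groups only. That stands, and it is why the point is minor.

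A reader might infer that the missing Hodges-Lehmann interval is part of the same contradiction, or that the SAP rules an interval out. The documents support neither. It is an omission unrelated to Levene's test, and nothing forbids reporting an interval. Section 1 already requires medians, IQRs and counts at each ordinal level by group and timepoint. These show spread, though not the precision of the between-group difference.

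**Conclusion.** The contradiction is real and confined to one situation: between-group comparisons of muscle size or ROM where normality is accepted and Levene gives p<=0.05. It is minor. With equal variances, the choice of section changes significance in well under 1% of all comparisons; the higher rates rest on assumed SD ratios. Where the sections conflict and the true effect is 1 SD, Welch rejects about 5 to 7 percentage points more often than Mann-Whitney, so following Section 3 would give a slightly worse result.

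A reader might infer that the primary results for these two domains are generally undetermined. They are not: in every other case the two sections agree. A reader might also infer, because enrolment is listed as actual and no adverse events are said to have been reported, that the test could be picked after seeing results. The documents suggest that data may exist; they do not show that any analysis preceded the SAP.

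The conclusion on the conflict rests on the text, not on the simulation. The absence of a Hodges-Lehmann interval is a reporting improvement, not an error.

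**What to change.** **Conflict.** In Section 3, delete *or homogeneity* and *or Levene's p<=0.05* from the non-parametric trigger, leaving Shapiro-Wilk p<=0.05 as the only formal trigger. Section 4.2 then governs: unequal variances lead to Welch's t-test, with the mean difference and its 95% confidence interval. The rank-based route for non-normal and ordinal data is unchanged.

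**Reporting, separately.** In Section 4.2, add *with 95% confidence intervals* after the Hodges-Lehmann differences.

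**Cost.** A few words and no new test. On the integer scales the Hodges-Lehmann limits will fall on whole points. That is coarse, particularly for the heavily tied 0-3 effusion and 0-5 strength scales, and how informative such intervals would be has not been assessed here. If data already exist, date both changes and report them as an amendment.
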